17.1 Patient Population

Female patients ages 18 or greater with Stages I-IIIc invasive carcinoma of the breast who receive mastectomy are eligible for this trial.

17.2 Potential Risks

Postmastectomy RT is routinely delivered to high risk subsets of women, including those with greater than 4 positive nodes, and those with 1-3 positive nodes and other adverse clinicopathological features. The side effects and risks of radiation therapy include fatigue, skin reaction/fibrosis, pain, lung inflammation/fibrosis, and secondary malignancy. With patients coming to treatment daily, we have adequate resources and support to assist patients in any manner, if required. The physician will evaluate the patient at least weekly to determine any routine or adverse side effects of the treatment. If adverse affects are seen, appropriate medical action will be taken.

17.3 Consent Procedures

Informed consent must be obtained prior to commencing any research procedures. The PI shall seek such consent only under such circumstances that provide the prospective patient opportunity to consider whether or not to participate and that minimizes the possibility of coercion or undue influence. The information given to the patient, or the representative, shall be in a language understandable to the subject or representative. The informed consent document may not include any exculpatory language through which the subject or representative is made to waive any of the subject's legal rights or

[REDACTED]
releases, or appears to release the investigator, the sponsor or the institution from liability for negligence.

17.4 Potential Benefits

The benefit of accelerated irradiation over conventional irradiation is the improved convenience of accelerated irradiation. More specifically, a conventional course of adjuvant post-mastectomy radiotherapy to 60 Gy would be delivered over 30 treatment days and over 42 calendar days (6 weeks). In contrast, a course of accelerated post-mastectomy radiation therapy as defined in this study would be delivered in 11-15 fractions over 15-19 days.

17.5 Risk-Benefit Ratio

The benefit of postmastectomy RT in improving overall survival, disease-free survival, and locoregional control rates is well documented. Multiple, large-scale prospective trials have demonstrated that the risks of radiation are modest, as described above, and do not outweigh the benefits of treatment. The goal of this study is to reproduce the excellent results of conventional post-mastectomy irradiation both in terms of efficacy (disease control) and toxicity (side-effects) using a more convenient, abbreviated course of post-mastectomy irradiation. As discussed above, the feasibility of this approach has been demonstrated by Yarnold⁵⁰, Formenti⁵⁷, and Whelan⁵¹ in their reports. Alternative treatments can include conventional chest wall irradiation, hormonal therapy alone, or no therapy. As already noted, the goal of the trial is to improve the convenience of radiation therapy using a shortened course of treatment, which may benefit women by improving quality of life. The accelerated fractionation scheme is expressly calculated to be biologically comparable to conventional irradiation in terms of efficacy and toxicity.

Appendix A

Information Template for Trial Submission to NJCTC

Protocol Title: Accelerated, Hypofractionated Post-Mastectomy Radiation Therapy in Women with Breast Cancer: A Phase II Trial

Brief Trial Description/Rationale:

This study is a non-randomized, single arm study of female patients with invasive carcinoma of the breast who have had (or will have) a mastectomy followed by radiation therapy. The term "accelerated" means that a higher radiation dose per treatment will be delivered over a shorter period of time (compared to the standard). Prior studies suggest that the accelerated radiation scheme used in this study is comparable to the standard or conventional whole breast radiation. That is, the evidence points to accelerated treatments may work at least as well as the longer, standard treatments. Along with measuring the treatment toxicity and recurrence outcomes, we will be recording the need for plastic reconstruction revisions (how well the study treatment plan preserves the appearance of your surgically reconstructed breast).

How long do you anticipate the protocol to be open?

Patients will be enrolled in this trial over the course of approximately 36 months. The duration of the protocol for each patient will be from the date of registration to the last day of radiation therapy. Patients will be followed regularly after treatment as per standard departmental policy. The duration of the study is estimated to be completed in 72 months.

Inclusion Criteria (main):

- Invasive ductal, medullary, papillary, colloid (mucinous), or tubular histologies. Invasive lobular carcinomas are allowed.
- AJCC Stage I – IIIc (pathologic stage T1-T4d, N0-N3, M0) histologically confirmed invasive carcinoma of the breast treated with mastectomy and either sentinel node biopsy or axillary dissection. Inflammatory carcinoma (T4d) is allowed.
- Multifocal/multicentric disease is allowed.
- Negative inked histologic margins of mastectomy (no invasive cells at margin) or positive margin at pectoralis fascia.
- Tamoxifen, Arimidex or other hormonal therapy is allowed. It may begin any time relative to the radiation at the discretion of the treating physician.
- Chemotherapy is allowed. If chemotherapy is indicated the chemotherapy can be delivered first, followed by radiation therapy beginning 21-63 days after the last cycle of chemotherapy or the radiation therapy can be delivered first and the chemotherapy can be delivered no earlier than 21 days post radiation therapy. Neoadjuvant chemotherapy is allowed; radiation therapy will be delivered after mastectomy or after any adjuvant chemotherapy as described above.

- Chest wall reconstruction is allowed.
- The patient must be enrolled and have treatment planning between 14 – 63 days from date of last surgery or last cycle of chemotherapy, and radiation must start within 21-63 days of date of last surgery or last cycle of chemotherapy.
- Women must be \geq 18 years of age.
- Signed study-specific informed consent form prior to study entry.

Exclusion Criteria (main):

- Patient with distant metastases (M1).
- Patients with ductal or lobular carcinoma in-situ alone (no invasive component) and patients with non-epithelial breast malignancies such as sarcoma or lymphoma.
- Palpable or radiographically suspicious contralateral axillary, supraclavicular, infraclavicular or internal mammary nodes, unless there is histologic confirmation that these nodes are negative for tumor.
- Prior radiation therapy to the chest.
- Patients with collagen vascular diseases, specifically systemic lupus erythematosis, scleroderma, or dermatomyositis.
- Patients with co-existing medical conditions with life expectancy $<$ 2 years.
- Patients with psychiatric or addictive disorders that would preclude obtaining informed consent.
- Other malignancy, except non-melanomatous skin cancer, $<$ 5 years prior to participation in this study; the disease-free interval from any prior carcinoma must be continuous.
- Women who are pregnant or lactating due to potential exposure of the fetus to RT and unknown effects of RT to lactating females.
- Women who are able to conceive and unwilling to practice and effective method of birth control. Women of childbearing potential must have a negative urine or serum pregnancy test within 7 days prior to treatment.

Appendix B

Performance Status Criteria

ECOG Performance Status Scale	
Grade	Descriptions
0	Normal activity. Fully active, able to carry on all pre-disease performance without restriction.
1	Symptoms, but ambulatory. Restricted in physically strenuous activity, but ambulatory and able to carry out work of a light or sedentary nature (e.g., light housework, office work).
2	In bed <50% of the time. Ambulatory and capable of all self-care, but unable to carry out any work activities. Up and about more than 50% of waking hours.
3	In bed >50% of the time. Capable of only limited self-care, confined to bed or chair more than 50% of waking hours.
4	100% bedridden. Completely disabled. Cannot carry on any self-care. Totally confined to bed or chair.
5	Dead.

Appendix C

DETERMINATION OF MENOPAUSAL STATUS

Menopausal Status Determination

The following criteria will be used to define *postmenopausal*:

- A prior documented bilateral oophorectomy, or
- A history of at least 12 months without spontaneous menstrual bleeding, or
- Age 55 or older with a prior hysterectomy, or
- Age 54 or younger with a prior hysterectomy without oophorectomy (or in whom the status of the ovaries is unknown), with a documented FSH level demonstrating confirmatory elevation in the lab's postmenopausal range.

Women failing to meet one of these criteria will be classified as pre-menopausal

Appendix D

Case Report Forms

CASE REPORT FORM #1 – PATIENT ENROLLMENT

Patient Identification:		  -    	Site	Sequential						
1. Enrollment Date:		  /   /  	M M	D D	Y Y	2. Date of Birth:	  /   /  	M M	D D	Y Y
3. Age at Diagnosis:		 	4. Menopausal Status:		 Pre	 Peri	 Post			
5. Race:		 Black	 Caucasian	 Hispanic	 Asian	 Other				
6. Histology:										
 Invasive ductal		 Pure DCIS		 Invasive lobular		 Other				
7. Grade:		 I	 II	 III						
8. AJC Classification:		Tis:		 T1	 T2					
		If T2, ≤ 3 cm		 Yes	 No					
9. Largest Tumor size:		  mm								
10. Surgical Margins:										
 Negative (no tumor on ink)		 Close (< 2 mm)		 ≥ 2 mm						
11. Nodes:		Negative	 Yes	 No	Numbered Excised:		Number positive:			
12. Sentinel node biopsied:		 Yes	 No	Axillary Dissection:		 Yes	 No			
13. Estrogen receptors – Positive: Value = _____				 Yes	 No	 Unknown				
14. Progesterone receptors – Positive: Value = _____				 Yes	 No	 Unknown				
15. Her2Neu – Positive:				 Yes	 No	 Unknown				
16. Adjuvant therapy for this cancer episode:										
 None		 Hormonal therapy type _____								
 Chemotherapy type _____		 Other _____								
17. Mastectomy Date (Last Surgery Date):		  /   /  	M M	D D	Y Y					
18. Lesion location:		 Left	 Right							
 UIQ		 LIQ	 Central	 UOQ	 LOQ					
19. Plastic reconstruction of treated side		 Yes	 No	If yes, before RT initiation?		 Yes or  No				
20. Type of reconstruction (if applicable, select all that apply):										
 Temporary Expander		 Prosthesis/Implant		 TRAM	 LAT	 DIEP	 SGAP/IGAP			

CASE REPORT FORM #2 – FOLLOW-UP VISITS

Patient Identification:	  -    	Site	Sequential																																																	
Date of Visit	  /   /  	M M D D Y Y	Scorer Name:																																																	

1. Complication Assessment (Must be evaluated at each visit)
 
 
 A Acute skin toxicity	 Not evident	 If Yes, complete CRF #3;	
 
 B Brachial plexopathy	 Not evident	 If Yes, complete CRF #4; Section I	
 
 C Acute lung toxicity	 Not evident	 If Yes, complete CRF #3;	
 
 D Pain	 Not evident	 If Yes, complete CRF #3&CRF #4; Section II	
 
 E Revision of plastic reconstruction	 Not evident	 If Yes, complete CRF #4; Section IV	
 
 F Fibrosis	 Not evident	 If Yes, complete CRF #3	
 
 G Other (Fatigue, Lung, Heart)	 Not evident	 If Yes, complete CRF #3&/or CRF#4,5 or 6	
 
 
2 Local failure:
 
 
  Scar	 Chest wall	 Inflammatory	 Biopsied	
 
 			 Invasive	
 
 			 Non-invasive	
 
 			 Grade _____	
 
 			 Receptor status _____	
 
 
3 Regional failure:
 
 
  Axilla	 Supraclavicular fossa	 Internal mammary nodes	 Skin	 Other	
 
 
4 Distant Failure
 
 
  Lung	 Bone	 Other	
 
				A Acute skin toxicity	 Not evident	 If Yes, complete CRF #3;	B Brachial plexopathy	 Not evident	 If Yes, complete CRF #4; Section I	C Acute lung toxicity	 Not evident	 If Yes, complete CRF #3;	D Pain	 Not evident	 If Yes, complete CRF #3&CRF #4; Section II	E Revision of plastic reconstruction	 Not evident	 If Yes, complete CRF #4; Section IV	F Fibrosis	 Not evident	 If Yes, complete CRF #3	G Other (Fatigue, Lung, Heart)	 Not evident	 If Yes, complete CRF #3&/or CRF#4,5 or 6	 Scar	 Chest wall	 Inflammatory	 Biopsied				 Invasive				 Non-invasive				 Grade _____				 Receptor status _____	 Axilla	 Supraclavicular fossa	 Internal mammary nodes	 Skin	 Other	 Lung	 Bone	 Other
A Acute skin toxicity	 Not evident	 If Yes, complete CRF #3;																																																		
B Brachial plexopathy	 Not evident	 If Yes, complete CRF #4; Section I																																																		
C Acute lung toxicity	 Not evident	 If Yes, complete CRF #3;																																																		
D Pain	 Not evident	 If Yes, complete CRF #3&CRF #4; Section II																																																		
E Revision of plastic reconstruction	 Not evident	 If Yes, complete CRF #4; Section IV																																																		
F Fibrosis	 Not evident	 If Yes, complete CRF #3																																																		
G Other (Fatigue, Lung, Heart)	 Not evident	 If Yes, complete CRF #3&/or CRF#4,5 or 6																																																		
 Scar	 Chest wall	 Inflammatory	 Biopsied																																																	
			 Invasive																																																	
			 Non-invasive																																																	
			 Grade _____																																																	
			 Receptor status _____																																																	
 Axilla	 Supraclavicular fossa	 Internal mammary nodes	 Skin	 Other																																																
 Lung	 Bone	 Other																																																		

CASE REPORT FORM #3 –ACUTE TOXICITIES (CTCAE v.3)

Patient Identification:			-					Site	Sequential
Date of Visit			/			/			Scorer Name:
	M	M		D	D		Y	Y	

RESPIRATORY ALTERATIONS

	1 ASYMPTOMATIC	2 SYMPTOMATIC NOT INTERFERING WITH FUNCTION	3 SYMPTOMATIC INTERFERING WITH FUNCTION	4 LIFE-THREATENING	COMMENTS
BRONCHOSPASM/WHEEZING					
COUGH (DRY, WET, BLOOD)	SYMPTOMATIC, NONNARCOTIC MEDICATION ONLY INDICATED	SYMPTOMATIC AND NARCOTIC MEDICATION INDICATED	SYMPTOMATIC AND SIGNIFICANTLY INTERFERING WITH SLEEP OR ADL		
DYSPNEA	DYSPNEA ON EXERTION, BUT CAN WALK 1 FLIGHT OF STAIRS OR 1 CITY BLOCK (0.1KM) WITHOUT STOPPING	DYSPNEA ON EXERTION BUT UNABLE TO WALK 1 FLIGHT OF STAIRS OR 1 CITY BLOCK (0.1KM) WITHOUT STOPPING	DYSPNEA WITH ADL	DYSPNEA AT REST; INTUBATION/VENTILATOR INDICATED	
VOICE CHANGES	MILD OR INTERMITTENT HOARSENESS OR VOICE CHANGE, BUT FULLY UNDERSTANDABLE	MODERATE OR PERSISTENT VOICE CHANGES, MAY REQUIRE OCCASIONAL REPETITION BUT UNDERSTANDABLE ON TELEPHONE	SEVERE VOICE CHANGES INCLUDING PREDOMINANTLY WHISPERED SPEECH; MAY REQUIRE FREQUENT REPETITION OR FACE-TO-FACE CONTACT FOR UNDERSTANDABILITY; REQUIRES VOICE AID (E.G., ELECTROLARYNX) FOR $\leq 50\%$ OF COMMUNICATION	DISABLING: NON-UNDERSTANDABLE VOICE OR APHONIC; REQUIRES VOICE AID (E.G., ELECTROLARYNX) FOR $>50\%$ OF COMMUNICATION OR REQUIRES $>50\%$ WRITTEN COMMUNICATION	

SKIN ALTERATIONS

	1 FAINT ERYTHEMA OR DRY DESQUAMATION	2 MODERATE TO BRISK ERYTHEMA; PATCHY MOIST DESQUAMATION, MOSTLY CONFINED TO SKIN FOLDS AND CREASES; MODERATE EDEMA MOIST DESQUAMATION OTHER	3 MOIST DESQUAMATION OTHER THAN SKIN FOLDS AND CREASES; BLEEDING INDUCED BY MINOR TRAUMA OR ABRASION	4 SKIN NECROSIS OR ULCERATION OF FULL THICKNESS DERMIS; SPONTANEOUS BLEEDING FROM INVOLVED SITE	COMMENTS
INDURATION/FIBROSIS	INCREASED DENSITY ON PALPATION	MODERATE IMPAIRMENT OF FUNCTION NOT INTERFERING WITH ADL; MARKED INCREASE IN DENSITY AND FIRMNESS ON PALPATION WITH OR WITHOUT MINIMAL RETRACTION	DYSFUNCTION INTERFERING WITH ADL; VERY MARKED DENSITY, RETRACTION OR FIXATION		
ATROPHY, SKIN	DETECTABLE	MARKED	--	--	--
ATROPHY, SUBCUTANEOUS FAT	DETECTABLE	MARKED	--	--	--
HYPERTIGMENTATION	SLIGHT OR LOCALIZED	MARKED OR GENERALIZED	--	--	--
HYPOPIGMENTATION	SLIGHT OR LOCALIZED	MARKED OR GENERALIZED	--	--	--
TELANGIECTASIA	FEW	MODERATE NUMBER	MANY AND CONFLUENT	--	--
ULCERATION		SUPERFICIAL ULCERATION <2 CM SIZE; LOCAL WOUND CARE; MEDICAL INTERVENTION INDICATED	ULCERATION ≥ 2 CM SIZE; OPERATIVE DEBRIDEMENT, PRIMARY CLOSURE OR OTHER INVASIVE INTERVENTION INDICATED (E.G., HYPERBARIC OXYGEN)	LIFE THREATENING CONSEQUENCES; MAJOR INVASIVE INTERVENTION INDICATED (E.G., COMPLETE RESECTION, TISSUE RECONSTRUCTION, FLAP OR GRAFTING)	--

[figure not shown]
ENERGY

	1 MILD FATIGUE OVER BASELINE	2 MODERATE OR CAUSING DIFFICULTY PERFORMING SOME ADL	3 SEVERE FATIGUE INTERFERING WITH ADL	4 DISABLING	COMMENTS
FATIGUE					

PAIN

	1 MILD PAIN NO INTERFERING WITH FUNCTION	2 MODERATE PAIN; PAIN OR ANALGESICS INTERFERING WITH FUNCTION, BUT NOT INTERFERING WITH ADL	3 SEVERE PAIN; PAIN OR ANALGESICS SEVERELY INTERFERING WITH ADL	4 DISABLING	COMMENTS
PAIN					

CASE REPORT FORM #4 - TOXICITIES									
Patient Identification:		  -    		Site Sequential					
Date of Visit		  /   /  		M M D D Y Y					
I BRACHIAL PLEXOPATHY									
1 Date of Onset: _____					 NOT APPLICABLE				
2 Method of detection (List all that apply):					Date of Resolution: _____				
 Clinical		 Physician		 Patient		 Imaging		 Other	
3 Symptomatic (List all that apply):									
 Pain		 Requiring non-narcotic analgesics		 Requiring narcotic analgesics		 Motor impairment		 Sensory impairment	
4 Method of treatment (List all that apply):									
 Observation		 Medication		 Physical therapy		 Surgical exploration		 Other	
II PAIN									
1 Date of Onset: _____					 NOT APPLICABLE				
2 Location of pain (List all that apply):					Date of Resolution: _____				
 Breast		 Axilla		 Chest wall		 Arm		 Other	
3 Degree of extent of pain (List all that apply):									
a Intensity: _____ (1-10; 1 = Least, 10 = greatest)					b Duration: _____ (1-10; 1 = Infrequent, 10 = constant)				
 Requiring only non-narcotic analgesics					 Requiring narcotic analgesics				
III TELANGIECTASIA									
1 Date of Onset: _____					 NOT APPLICABLE				
2 Degree:					Date of Resolution: _____				
 Grade 1 (< 9 cm ²)		 Grade 2 (9 - 36 cm ²)		 Grade 3 (> 36 cm ²)		 Grade 4 (Whole Field)			
IV REVISION OF PLASTIC RECONSTRUCTION									
1 Date of Onset: _____					 NOT APPLICABLE				
2 Degree:					Date of Resolution: _____				
 G ₁ (localized)					 G ₂ (Generalized)				

CASE REPORT FORM #5 – CHEST WALL LATE TOXICITIES

Patient Identification:	  -    	Site Sequential
Date of Visit	  /   /  	M M D D Y Y
I LATE TOXICITY – SKIN (RTOG/EORTC)		
 Grade 0	 Not done	
 Grade 1	None	
 Grade 2	Slight atrophy; pigmentation change; some hair loss	
 Grade 3	Patch atrophy; moderate telangiectasia; total hair loss	
 Grade 4	Marked atrophy; gross telangiectasia	
 Grade 5	Ulceration	
 Grade 5	Death	
II LATE TOXICITY – SUBCUTANEOUS (RTOG/EORTC)		
 Grade 0	 Not done	
 Grade 1	None	
 Grade 2	Slight induration (fibrosis) and loss of subcutaneous fat	
 Grade 3	Moderate fibrosis but asymptomatic; slight field contracture < 10% linear reduction	
 Grade 4	Severe induration and loss of subcutaneous tissue Field contracture > 10% linear measurement	
 Grade 5	Necrosis	
 Grade 5	Death	

CASE REPORT FORM #6 – HEART/LUNG LATE TOXICITIES

Patient Identification:	  -    	
	Site	Sequential
Date of Visit	  /   /  	
	M M D D Y Y	
I LATE TOXICITY – LUNG (RTOG/EORTC)		
 Grade 0	 Not done	
 Grade 1	None	
 Grade 2	Asymptomatic or mild symptoms (dry cough) Slight radiographic appearances	
 Grade 3	Moderate symptomatic fibrosis or pneumonitis (severe cough); low grade fever Patchy radiographic appearances	
 Grade 4	Severe symptomatic fibrosis or pneumonitis Dense radiographic changes	
 Grade 5	Severe respiratory insufficiency/continuous O ₂ /assisted ventilation Death	
II LATE TOXICITY – HEART (RTOG/EORTC)		
 Grade 0	 Not done	
 Grade 1	None	
 Grade 2	Asymptomatic or mild symptoms Transient T wave inversion & ST changes Sinus tachycardia>110 (at rest) Moderate angina on effort	
 Grade 3	Mild pericarditis; normal heart size; persistent abnormal T wave and ST changes Low QRS Severe angina	
 Grade 4	Pericardial effusion; constrictive pericarditis; moderate heart failure; cardiac enlargement EKG abnormalities Tamponade; severe heart failure Severe constrictive pericarditis	
 Grade 5	Death	

EXPIRE

APPROVED

OCT 17

Approved by

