IBRT	Ipsilateral Breast Tumor Recurrence
IBTR	Ipsilateral Breast Tumor Recurrence
IRB	Institutional Review Board
IMRT	Intensity Modulated Radiation Therapy
LFS	Local Recurrence-Free Survival
LR	Loco-regional
MR	Marginal Recurrence
NCI	National Cancer Institute
NIH	National Institutes of Health
NSABP	National Surgical Adjuvant Breast and Bowel Project

Accelerated, Hypofractionated Post-Mastectomy RT in Women with Breast Cancer: A Phase II Trial

OHRP	Office of Human Research Protection
OHRS	Office of Human Research Services
PBI	Partial Breast Irradiation
PD	Progressive disease
PHI	Protected Health Information
PI	Principal Investigator
PTV	Planning Target Volume
RL	Right-Left
RT	Radiation Therapy
RTOG	Radiation Therapy Oncology Group
RWJUH	Robert Wood Johnson University Hospital
SAE	Serious adverse event
TR	True Recurrence
TR/MM	True Recurrence/Marginal Miss
WBI	Whole Breast Irradiation

1. Purpose/Specific Objectives

1.1 Primary Endpoint:

The results from this novel fractionation scheme will be comparable to published locoregional control outcomes for conventionally fractionated chest wall irradiation.

- 1.1.1 Acute toxicity and late toxicity using previously published toxicity scales.

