4.1 Duration of Study

Patients will be enrolled in this trial over the course of approximately 36 months. The duration of the protocol for each patient will be from the date of registration to the last day of radiation therapy. Patients will be followed regularly after treatment as per standard departmental policy (Section 9.2.1). The duration of the study is estimated to be 72 months, such that the minimum follow-up in the study cohort is 36 months.

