5.6 Study Enrollment Procedures

Accelerated, Hypofractionated Chest Wall Radiotherapy in Women with Breast Cancer: A Phase II Trial
 [REDACTED]

6. Study Parameters

Evaluations	Prior to treatment	During Radiation (weekly)	FOLLOW-UP (after radiation therapy)		
			End of Radiation and 2-8 weeks after RT	Then every 3-9 months (for 3 yrs)	Then every 6-15 months (out to 5 yrs)
Signed informed consent	X				
History & Physical	X	X	X	X	X
Pregnancy test (B-HCG)	X ¹				
Chest wall CT (Simulation)	X ²				
Optional serum and tumor tissue samples	X ³				

1. Within 7 days before starting treatment if of child bearing age. For menopausal status, see Appendix C.

2. After surgery/chemotherapy for treatment planning

3. For optional correlative studies, patients will be offered co-enrollment in CINJ Study # 040703 (IRB 0220070169). See Sections 9.4 and 11.

4. End of radiation = During the last 3 fractions of radiation

7. Treatment Plan

Postmastectomy RT consists of 3663 cGy in 11 fractions (333 cGy) over 11 weekdays (for 15 elapsed days); no boost is required, optional chest wall boost upto 4 fractions of 3.33 cGy is allowed (total 1332 cGy).

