8.4 Definition of Unexpected Adverse Events

8.4.1 Any adverse drug experience and/or specificity, that is not included in the current investigator's brochure and/or package insert.

9. Treatment Evaluation/Criteria for Response

- ◊ Loco-regional (LR) control will be assessed by physical examination and other relevant imaging per the discretion of the patients treating physicians. All LR failures have to be confirmed by biopsy, and should be coded as either chest wall recurrence, axilla, supraclavicular, or internal mammary.

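### CRF #6 grades late heart and lung toxicity partly by ECG and imaging that follow-up does not schedule, so untested and tested-normal patients are recorded alike and any-grade late rates can be under-counted

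*Combined protocol and SAP*

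**What the plan says.** Section 1.1.1, under the primary endpoint, reads "Acute toxicity and late toxicity using previously published toxicity scales".

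Appendix D, CRF #6, is the form for late lung and heart toxicity (RTOG/EORTC). Its heart levels mix symptoms with test findings, for example "Transient T wave inversion & ST changes Sinus tachycardia>110 (at rest"; other levels refer to low QRS, heart size, pericardial effusion and cardiac enlargement. Its lung levels pair symptoms with increasingly marked radiographic change, starting at "Asymptomatic or mild symptoms (dry cough) Slight radiographic appearances". Both parts have a *Not done* box that is separate from *None*.

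In the Section 6 table the only evaluation marked after radiotherapy is "History & Physical". The only imaging row is the simulation CT, with the footnote "After surgery/chemotherapy for treatment planning". Section 4.1 adds: "Patients will be followed regularly after treatment as per standard departmental policy". Section 9 mentions later imaging, but for another purpose: "Loco-regional (LR) control will be assessed by physical examination and other relevant imaging per the discretion of the patients treating physicians".

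CRF #2, item 1, must be evaluated at each visit. Its row "G Other (Fatigue, Lung, Heart") offers two answers: *Not evident*, or a yes that sends the user to CRF #3 to #6.

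Section 16.6 imputes missing data from the study population as a whole.

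**The concern.** Part of the CRF #6 scale can be filled in only if someone has taken a tracing or an image, and the protocol does not ask for one. The form that leads to CRF #6 has no answer for a patient who was not tested. Absence of a finding and absence of a test then produce the same record.

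What is at stake is the reporting of late toxicity under Section 1.1.1. An any-grade late heart or lung rate computed over all patients would depend on how often patients happened to be tested as well as on how often the change occurred. The error runs in the reassuring direction, in a study whose Section 16.1 hypothesis is that toxicity is similar to that of standard treatment.

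**Working it through.** **1. Is the tested toxicity rule touched?** Inputs from Section 16.2: n = 67, reject a 3% rate at 5 or more events, alternative 9%.

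- Significance level = P(X ≥ 5), X ~ Binomial(67, 0.03) = 0.0508. The plan states 0.0508.
- Power = P(X ≥ 5), X ~ Binomial(67, 0.09) = 0.7316. The plan states 0.732.
- Stopping table, uniform prior: P(rate > 9%) = 0.813 for 4 of 33 and 0.633 for 3 of 33. Both match.

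The Section 16.2 event consists of chest-wall pain of grade 3 or more, painful or symptomatic brachial plexopathy, and symptomatic acute pneumonitis of grade 3 or more. No late heart or late lung item is in it, so none of these figures changes.

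**2. What can be seen without a test?** This step uses the CRF #6 descriptors only, because grade numbers and descriptors may not line up in the copy read.

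| CRF #6 | History and physical can detect | Needs a tracing or image |
|---|---|---|
| Lung | cough, fever, symptomatic fibrosis or pneumonitis, respiratory insufficiency | slight, patchy or dense radiographic change |
| Heart | angina, symptomatic heart failure, a fast resting pulse | T-wave and ST changes, low QRS, heart size, effusion |

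The lowest abnormal level in each organ includes asymptomatic patients. For them the right-hand column is the only evidence.

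**3. What is recorded for an asymptomatic patient?**

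| Patient | CRF #2 row G | CRF #6 | *Not done* reached? |
|---|---|---|---|
| Tested, abnormal | yes | completed | not needed |
| Tested, normal | *Not evident* | not opened | no |
| Never tested | *Not evident* | not opened | no |

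The last two rows cannot be told apart. *Not evident* is a completed answer, so nothing is missing and the Section 16.6 imputation is not triggered. Section 8 gives no other route: its adverse-event recording ends 30 days after the last treatment.

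**4. Direction and size.** Let π be the share of patients with a change visible only on a test, and t the share of those patients who were tested. Over all patients,

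reported share = π × t ≤ π.

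The documents give neither π nor t. Purely as assumed values:

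| π | t = 10% | t = 50% |
|---|---|---|
| 20% | 2% | 10% |
| 40% | 4% | 20% |

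The formula needs t only among patients who have the change, so it does not require testing to be unrelated to toxicity.

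**5. Does dividing by tested patients solve it?** Assume 34 of 67 are tested and 7 have a finding. Then 7/67 = 10.4% and 7/34 = 20.6%. With 33 patients unknown, the true share lies anywhere from 7/67 = 10.4% to (7 + 33)/67 = 40/67 = 59.7%. The 20.6% is valid only if testing is unrelated to the finding, which is doubtful when tests are ordered for a reason.

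**The case against.** The strongest reply is that this does not reach the trial's decision. Section 16.2 omits late heart and lung toxicity, Section 9.1.2 does not list them among its additional endpoints, and Section 16.4 even places toxicity among the secondary endpoints. That stands. A reader might infer that untested patients count as toxicity-free in the primary test; step 1 shows they do not enter it. Nor does any text say that *Not evident* is analysed as grade 0. The point is about what the record can distinguish.

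Second, CRF #6 has a *Not done* box, and row G may be a loose prompt rather than a strict gate: it is also the only row that points to the late skin form, CRF #5. Section 13.1 refers to a data capture plan that is not included. The flow in step 3 is thus an inference from the forms, but these documents show no other route to CRF #6.

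Third, much of the scale is symptomatic and can be found at a visit. This is correct and limits the gap to test-defined levels.

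Two further inferences are tempting. One is that the rates will be biased against published ones. That requires the published series to have tested patients systematically, which the documents do not say; if those series also relied on clinical detection, the comparison need not be biased. The other is that the Fisher tests in Section 16.5 will find predictors of testing. That section names toxicity in general and not these grades, so this is speculation.

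**Conclusion.** The point holds for descriptive late-toxicity reporting under Section 1.1.1, and only for levels that rest on an ECG or image. As the forms stand, any-grade late heart and lung rates over all 67 patients can be too low and cannot be too high for this reason. The amount cannot be computed; the figures in steps 4 and 5 are illustrations under assumed rates. The conclusion rests on two readings: that Section 6 lists all scheduled follow-up evaluations, and that CRF #6 is opened only through row G.

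The Section 16.2 event, n = 67, the rule of 5 or more events and the stopping table stand as they are. This is a worthwhile, cheap correction and not a flaw in the primary test.

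**What to change.** No new tests are needed.

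1. State in Section 16.4 that the reported late heart and lung outcome is the set of symptomatic levels on CRF #6 that a history and physical can detect, with all treated patients as the denominator.
2. Instruct sites to complete CRF #6 at every follow-up visit, ticking *Not done* where no ECG or imaging was obtained. State in Section 16.6 that these entries are not imputed.
3. Report findings that rest on ECG or imaging alone as number found and number tested, with a note that tested patients are selected. State that any-grade late heart and lung rates will not be compared with published rates.

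The cost is one more form per visit. On the Section 6 intervals that is about 6 to 16 forms for a patient followed to five years: 36/9 = 4 to 36/3 = 12 in the first three years, plus 24/15 = 1.6 to 24/6 = 4 in the next two. The study also gives up an all-patient estimate for asymptomatic changes, which the present schedule could not support.
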